5.7.1.1. Model Assumption Checks

In order to check the homogeneity of treatment effect across strata, the treatment differences and corresponding 95% CI will be calculated and graphically presented for each stratum h , following the same continuity correction method for variance as in the primary approach.

5.7.1.2. Supportive Analyses for the Primary Efficacy Endpoint

The following statistical analyses will be used to further assess the primary efficacy endpoint. As appropriate, p values will be provided for descriptive purpose only.

Sensitivity to small event rate

The adequacy of the CMH statistics may be of concern in the case of an unexpectedly very small event rate. The Fisher's exact test is valid regardless of the cell sizes and therefore will be employed as a supportive statistical approach to confirm the results from the primary approach.

The Fisher's exact test will be applied to the whole FAS for comparisons of each REGN2222 arm to placebo. The number of subjects with primary endpoint event(s) will be $(\diamond_i + \diamond_i \times \diamond_i)$ endpoint event(s) in treatment group i (including LP subjects who had their primary endpoint missing but died prior to Day 150 due to causes adjudicated to be RSV related), \diamond_i is the number of early termination subjects **missing** the primary endpoint in treatment group i , and \diamond_i is the KM

estimate of the primary endpoint event rate in all subjects randomized to the placebo group.

The Fisher's exact test will also be applied to subgroups defined by stratification variables (ie, test in the subgroups of North America, rest of the world, ≤ 31 weeks 6 days GA, and $GA \geq 32$ weeks 0 days and < 35 weeks 6 days, respectively). The number of subjects with primary endpoint event(s) in each of the subgroups will be calculated in the same fashion as for the whole FAS except that \diamond_i and \diamond_i will be stratified group specific. This analysis will only be performed if there are enough subjects in each stratification level.

The SAS FREQ procedure with the option FISHER in the TABLE statement will be used to compute the 2-sided p-value of the Fisher's exact test.

In order to check the homogeneity of treatment effect across strata, the Fisher's exact test will also be run for each stratum h .

Regression method adjusting for covariates

The primary approach based on the CMH statistics tests for absolute difference in proportions between treatment groups. As a supportive approach, the logistic regression will use odds ratio to test for relative treatment effect of each REGN2222 arm over placebo on the primary efficacy variable. The number of subjects with primary endpoint event(s) will be $(n_{ih} + n_{ih} \times \theta_{ih})$ rounded to its nearest integer for treatment group i within each stratum h (a total of 4 strata as defined in the primary approach). The model for the logistic regression will include treatment group, region and gestational age category as factors. The maximum likelihood (ML) estimates of the odds ratio, and asymptotic normality based 95% CIs and p-values will be computed using the SAS LOGISTIC procedure. In the event that quasi-complete separation of data points occurs (ie, the outcome variable separates a predictor variable or a combination of predictor variable to an almost full degree), Firth's penalized likelihood approach may be employed to reduce bias in logistic regression. This approach will use the SAS LOGISTIC procedure with option=Firth.

In order to check the homogeneity of treatment effect across strata, the terms of interaction between treatment and strata (ie, region and gestational age group) will be added to the logistic regression model to obtain p values for the interaction terms for descriptive purpose. Stratum specific odds ratios and 95% CIs will also be reported.

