#### **Statistical Plan**

#### Sample Size

**For Part A:** The goal is to confirm infant PK and therefore no formal sample size calculation will be conducted. A total of 24 subjects will receive REGN2222 in Part A as this is considered a sufficient number of subjects to confirm PK parameters.

**For Part B:** A total of 1515 subjects are planned to enroll in Part B. Subjects will be randomly assigned in a 1:1:1 ratio (505 subjects in each arm for a total of 1010 assigned to receive REGN2222 [505 subjects in each of the 2 REGN2222 arms] and 505 subjects to receive placebo).

There will be at least 90% power to detect the difference between either dose of REGN2222 and placebo using a chi-square test with continuity correction at 2-sided test alpha=0.025 for each comparison between treatment group and placebo assuming the following: a placebo incidence rate of the primary endpoint of 10% and an efficacy of REGN2222 of at least 60% in reducing the rate of the primary endpoint compared with placebo and 5% early dropout rate.

Sample size may be re-estimated at the end of each RSV season. If the study is fully enrolled at that time, then the sample size will be re-estimated before database lock. Sample size re-estimation will be based on the blinded and pooled event rate and hypothesized treatment effect. The hypothesized treatment effect for each arm of REGN2222 will be a 60% reduction in event ratescomparedwiththeplaceboarm. The blinded sample size re-estimation

does not affect type I error materially for binomially distributed data. The objective of this sample size re-estimation is to ensure that the study is adequately powered in case of a milder-than-expected RSV season, leading to low medically attended visits for RSV infection.

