2. INVESTIGATION PLAN

2.1. Study Design and Randomization

This is a Phase 3 study that will be conducted in 2 parts.

Part A was an open-label, single cohort, multicenter, PK study.

Part B is a randomized, placebo-controlled, 3-arm, multicenter study. In Part B, the sponsor (Regeneron Pharmaceuticals, Inc.) will provide permitted windows for prophylaxis of subjects in each geographical area based on historical data on the timing and duration of the RSV season. A total of 3 treatment arms (1 dose of REGN2222 and 1 dose of placebo; 2 doses of REGN2222; and 2 doses of placebo) with a total of 1515 subjects are planned in Part B and will be randomized in a 1:1:1 ratio (505 subjects in each arm for a total of 1010 assigned to receive REGN2222 [505 subjects in each of the 2 REGN2222 arms] and 505 subjects to receive placebo). Randomization will be stratified by region (North America or rest of the world) and GA (≤ 31 weeks, 6 days GA or from 32 weeks, 0 days to 35 weeks, 6 days GA).

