2.2. Sample Size and Power Considerations

Originally Planned Sample Size

For Part B, the sample size estimation is based on the primary efficacy endpoint of medically attended RSV infection (hospitalization or outpatient LRTI). Literature ([Hall 2009](#), [Ambrose 2014](#)) show that the event rate in this endpoint is in the range of 12% to 22% in the studied infant populations. The Hall data is population based and the majority of infants are full-term; the Ambrose publication of data from the RSV Respiratory Events Among Preterm Infants Outcomes and Risk Tracking (REPORT) study evaluated preterm infants of 32-35 weeks gestational age and less than 6 months of chronological, whom were not receiving RSV prophylaxis. As the event rate may vary over RSV season or geographic region, a relatively conservative approach was taken to assume that event rate is 10% for the placebo group, and either dosing regimen of REGN2222 would reduce the event rate from placebo by 60% (event rate of 4%). With 505 randomized subjects per arm or a total of 1515 randomized subjects, the study would have 90% power to demonstrate a 60% or greater reduction at 2-sided significance level $\alpha=0.025$. This originally planned sample size also incorporated a 5% early dropout rate. The sample size calculation was based on chi-square test with continuity correction and performed using nQuery version 7.0 (Statistical Solutions Ltd, Cork, Ireland).

Based on the originally planned sample size and event rate assumption, we anticipated approximately 90 primary endpoint events.

The blinded sample size re-estimation (as detailed in the study protocol Section 9.2.1) designed for the originally planned sample size has not been performed for this study.

Power Calculation for Reduced Sample Size

[figure not shown]
The sample size of the study has been reduced due to business considerations. The intent of this power calculation is to understand the impact of the reduced sample size on the primary efficacy analysis. Specifically, to accommodate the reduced sample size, the overall Type I error for the pairwise comparisons of each REGN2222 dose regimen to placebo will be controlled using a

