Missing Data Handling for the Primary Efficacy Endpoint

For early termination (ET) subjects those who did not complete the 150-day efficacy assessment period, their primary endpoint will be handled according to the following rules in the primary analysis:

- Early termination subjects who had a primary endpoint event during the 150-day efficacy assessment period (regardless of treatment status, ie, whether the subject received all study drug doses or discontinued dosing) will be used in the primary analysis and included as “event occurred”. [Observed, thus no imputation]
- Direct imputation of missing primary endpoint at Day 150 visit:
 - Subject deaths prior to Day 150 that are adjudicated to be RSV related will be included as “event occurred” at the onset date of the adverse event that led to death.
 - Remaining early termination subjects (including non-RSV deaths) across all treatment groups, will be imputed to the average placebo score (estimated placebo event rate).
 - Approach to estimating the placebo event rate is the Kaplan-Meier (KM) estimate at Day 150 based on all randomized subjects in the placebo group. Early termination subjects in the placebo group who had no primary endpoint event will be censored in the KM procedure at the last time point when their primary endpoint event is assessed (ie, at the last visit completed by the subject, scheduled or unscheduled, prior to Day 150 visit). Placebo subjects who completed Day 150 visit with no primary endpoint event will be censored at the date of their Day 150 visit. The derivation of study day is detailed in Appendix 11.3.
- Imputed scores along with observed subject data will be utilized in the Cochran-Mantel-Haenszel (CMH) analysis.

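### The supportive logistic regression rounds imputed events to whole numbers within each arm and stratum, so it does not carry the imputation used in the primary analysis

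*SAP*

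**What the plan says.** SAP 4.6.1 sets the missing-data rule. Early-termination infants with neither an observed event nor an RSV-related death, in every arm, "will be imputed to the average placebo score (estimated placebo event rate"), and that rate is the placebo Kaplan-Meier estimate at Day 150. SAP 5.7.1 puts the resulting fractional counts into the stratum proportions of the primary Cochran-Mantel-Haenszel (CMH) analysis and states no rounding.

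SAP 5.7.1.2, under the regression method, adds observed and imputed events but has the sum "rounded to its nearest integer for treatment group" i within stratum h, with "a total of 4 strata as defined in the primary approach". The model has treatment, region and gestational-age category, fitted by maximum likelihood with a Firth fallback. The same paragraphs ask for treatment-by-stratum interaction p-values and stratum-specific odds ratios. SAP 5.7.2 repeats the supportive analyses for the secondary endpoint.

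The formula symbols in 5.7.1.2 are not legible in the text available for this review. They are read here from the definitions in 5.7.1: observed events plus missing infants times the placebo rate.

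**The concern.** The regression is there to show that the primary result survives a change of effect measure and model. That comparison is clean only if both analyses use the same data. Observed counts are already whole numbers, so rounding alters only the imputed part, and that part is well below one event in most strata. Whether a stratum's imputation vanishes or becomes a whole event then depends on how dropouts happen to fall. A difference between the regression and the primary analysis, or between strata, could come partly from rounding and be read as model sensitivity or heterogeneity.

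**Working it through.** **Inputs.** Placebo rate: the SAP chose to "assume that event rate is 10% for the placebo group" (2.2), with 4% on REGN2222. Dropout: "This originally planned sample size also incorporated a 5% early dropout rate" (2.2). Size: about 1200 treated infants in three equal arms (2.2), so about 400 per arm. Stratum sizes and missing counts per stratum are not in the documents and are assumed below.

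**Design figures reproduced.** For 10% versus 4%, continuity-corrected chi-square, two-sided 0.025 and 90% power, the formula gives 479.4 evaluable per arm. 479.4/0.95 = 504.6, against 505 stated (506 if 479.4 is first rounded up to 480). With 400 × 0.95 = 380 evaluable per arm at two-sided 0.05, power is 87.4%, against about 87% stated. The inputs are therefore read as the SAP intends.

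**Expected imputation.** Missing per arm: 400 × 0.05 = 20. Imputed events per arm: 20 × 0.10 = 2.0. Average per stratum: 2.0/4 = 0.5.

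**What rounding does in one arm-by-stratum cell at a rate of 0.10.**

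| Missing | Imputed | After rounding | Ratio |
|---|---|---|---|
| 1-4 | 0.1-0.4 | 0 | 0 |
| 5 | 0.5 | 1 | 2.00 |
| 6 | 0.6 | 1 | 1.67 |
| 7 | 0.7 | 1 | 1.43 |
| 8 | 0.8 | 1 | 1.25 |
| 9 | 0.9 | 1 | 1.11 |
| 10 | 1.0 | 1 | 1.00 |
| 11-14 | 1.1-1.4 | 1 | 0.91-0.71 |

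At other placebo rates, the largest missing count that still rounds to zero is 8 at 6%, 6 at 8% and 4 at 12%.

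**Effect on the fitted model.** Assumed: 400 per arm, equal strata, 38 versus 15 observed events (380 × 0.10 = 38; 380 × 0.04 = 15.2), model with treatment, region and gestational age.

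| Missing per stratum, each arm | Imputed per arm, fractional / rounded | OR fractional | OR rounded |
|---|---|---|---|
| 5 | 2.0 / 4 | 0.399 (95% CI 0.222-0.717) | 0.425 (0.243-0.745) |
| 4 | 1.6 / 0 | 0.394 | 0.371, the same as no imputation |

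**Scatter across strata.** With 20 missing per arm allocated at random (200,000 draws) under assumed splits of 25/25/25/25, 20/40/10/30 and 10/40/10/40%, and in runs where the dropout number also varied:

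- about 41-49% of cells with missing data lose all imputation;
- the arm total shifts by -1 to +1 event (5th-95th percentile);
- the ratio of rounded to fractional odds ratio has a central 95% range of about 0.91-1.10. Letting observed events vary as well gave 0.89-1.09 (equal strata) and 0.92-1.06 (10/40/10/40);
- nominal p<0.05 status changed in 1.4% to 4.4% of simulated trials (active rate 4% or 6%).

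At a placebo rate of 6-8% the shift is mostly deletion, on average 0.1 to 1.0 event lost per arm. That moves the regression towards the no-imputation answer, which in the table above lies further from 1.

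**A single stratum.** Assumed: 100 per arm, 10 versus 4 observed events. With 4 placebo and 5 active infants missing, the rounded OR is (5/95)/(10/90) = 0.474 and the fractional OR is (4.5/95.5)/(10.4/89.6) = 0.406. With 5 and 4 missing, they are (4/96)/(11/89) = 0.337 and (4.4/95.6)/(10.5/89.5) = 0.392. A change of one dropout in each arm moves the rounded value from 0.474 to 0.337, and the fractional value only from 0.406 to 0.392.

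**The case against.** The strongest reply is that little depends on this. The confirmatory test is the CMH analysis, which keeps fractions. SAP 5.7.1.2 makes the supportive p-values descriptive. Cell errors partly cancel: under the 20/40/10/30 split about 65% of arms have no net shift, and a one-event shift in the active arm alone moves an OR of 0.40 only to 0.375 or 0.424, inside a confidence interval of about 0.22-0.72. Missing-data sensitivity is also examined elsewhere: the observed-case and tipping-point analyses (5.7.1.3), stratum differences by the primary method (5.7.1.1), and a Cox model with censoring (5.7.4). All of this stands and keeps the point minor.

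None of those analyses gives the odds ratio under the rule in 4.6.1, however. Odds ratio and risk difference are different measures, which is a reason to hold the data fixed when comparing them. Logistic regression does not need whole-number counts.

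A reader might infer that rounding generally doubles the imputation, or that an odds ratio of 0.40 could become 0.33 or 0.48. The documents do not support either. Doubling needs exactly 5 missing infants at a rate of exactly 0.10; at 0.095 the same 5 round to zero. The values 0.33 and 0.48 need opposite two-event shifts in the two arms. At a rate of 0.10 a cell can lose at most 0.4 event, so four cells lose at most 1.6, and with 20 missing per arm no such pair occurred in 200,000 draws. Even opposite one-event shifts (0.365 or 0.436) occurred in at most about 5%.

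**Conclusion.** The point holds as a minor inconsistency between the supportive regression and the analysis it supports. At the SAP's own design values the imputed part averages half an event per stratum, so rounding often removes it or turns it into a whole event. Expect an arm total off by no more than about one event and an overall odds ratio changed by up to about 10%. The hard limit is 0.5 event per cell and 2 events per arm. Stratum-specific odds ratios and interaction tests are the most exposed.

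These sizes rest on 5% dropout, a 10% placebo rate and assumed stratum splits. A placebo rate of 6-8% shifts the effect mainly towards deletion. It would be wrong to conclude that the primary result or the type I error is at risk: the CMH test does not round, and the p-values affected are descriptive.

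**What to change.** In SAP 5.7.1.2, delete the rounding for the logistic regression. Enter each early-termination infant with a missing endpoint as two records: an event with weight equal to the placebo Kaplan-Meier rate, and a non-event with weight one minus that rate. All other infants, including RSV-related deaths counted as events, get one record with weight 1. Keep the model terms, the maximum-likelihood estimation and the interaction and stratum-specific outputs as stated; robust standard errors are not needed for this change. Apply the same wording to the secondary endpoint under 5.7.2.

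The cost is a weight variable, a sentence of SAP text before database lock, and a check that the Firth fallback runs with weights. No data collection changes.

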5.7.1.3. Sensitivity to the Handling of Missing Data

The following analyses will be conducted to assess the results from the primary analysis with regards to the handling of missing data. As appropriate, p values will be provided for descriptive purpose only.

Observed-Case Analysis

In the observed-case analysis, for each treatment group, the proportion of subjects considered to have primary endpoint event occurrence will be calculated with the numerator being the number of subjects with observed primary endpoint event(s) (including ET subjects who had their primary endpoint missing but died prior to Day 150 due to causes adjudicated to be RSV related), and the denominator being the number of subjects in the FAS. The observed-case based proportion difference will be calculated for each stratum h and then combined across strata to generate the CMH statistics following the same method as in the primary approach.

Tipping Point Analysis

A tipping point analysis will be employed to explore the degree of shift from the placebo event rate used in the imputation of missing data in REGN2222 arms. The tipping point analysis will include the following steps to impute missing primary endpoint at Day 150 visit:

1. Subject deaths prior to Day 150 that are adjudicated to be RSV related will be included as "event occurred".
2. Remaining early termination subjects (including non-RSV deaths) in the **placebo** group will be imputed to the average placebo score (ie, the KM estimate of the primary endpoint event rate in all subjects randomized to the placebo group).
3. Remaining early termination subjects (including non-RSV deaths) in the **REGN2222** arm will be imputed to $\delta \times n_{ih} \times \theta_{ih} / g_{ih}$, where $\delta = 2$. (Note: $\delta = 1$ is equivalent to the primary analysis)

4. Repeat the step 3 with $\delta = 3, 4, 5$, etc. until reaching the point that the treatment effect of REGN2222 will be lost (ie, the difference [REGN2222 – placebo] in the proportion of subjects with primary endpoint event[s] is ≥ 0).

The tipping point analysis will be conducted for the pairwise comparisons of each REGN2222 arm to placebo separately, using the same CMH statistics as in the primary approach.

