# 9.2. Sample Size

For Part A, the goal of the study is to study infant PK, and therefore no formal sample size calculation will be conducted.

For Part B, the sample size estimation is based on the primary efficacy endpoint of medically attended RSV infection (hospitalization or outpatient LRTI). Literature (Hall 2009, Ambrose 2014) show that the event rate in this endpoint is in the range of 12% to 22% in the studied infant populations. As the event rate may vary over RSV season or geographic region, it is assumed that event rate is 10% for the placebo group, and either dose of RENG2222 would reduce the event rate from placebo by 60% (event rate of 4%). With 505 randomized subjects per arm or a total of 1515 randomized subjects, the study has 90% power to demonstrate a 60% or greater reduction at 2-sided significance level  $\alpha$ =0.025. This sample size also incorporated a 5% early dropout rate. The sample size calculation is based chi-square test with continuity correction and performed using nQuery version 7.0 (Statistical Solutions Ltd, Cork, Ireland).

The significant level of 2-sided 0.025 is set in consideration of multiplicity of 2 comparisons between each of the 2 REGN2222 dose arms with placebo.

With a total of 1515 randomized subjects and 1:1:1 randomization ratio, it is expected 1010 subjects to receive REGN2222 (505 subjects in each of the 2 REGN2222 arms) and 505 subjects to receive placebo and in total, an approximate of 90 primary endpoint events. Also, with 1010 subjects exposed to REGN2222, the regulatory requirement for safety assessment will be met.

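### The SAP's tipping-point rule has no upper bound on the imputed event probability, and at the design values it stops at an impossible 1.3 events per missing infant.

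*SAP*

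**What the plan says.** SAP 5.7.1.3 sets out the tipping-point analysis in four steps. Deaths adjudicated as RSV-related count as events. Other early terminations on placebo receive the placebo Kaplan-Meier rate. Other early terminations on REGN2222 receive a score scaled by delta, starting at 2, with a note that delta = 1 gives back the primary analysis. Delta then goes to 3, 4, 5 and onward "until reaching the point that the treatment effect of REGN2222 will be lost", which the SAP defines as a REGN2222 minus placebo difference of zero or more. The visible text gives no upper limit for delta or for the imputed score. It also does not say what to report if no possible score meets the criterion.

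The planning values are in Protocol 9.2 and SAP 2.2. On the placebo rate: "it is assumed that event rate is 10% for the placebo group". REGN2222 is assumed to reduce it by 60%, to 4%. On dropout: "This originally planned sample size also incorporated a 5% early dropout rate". SAP 2.2 also gives the reduced enrolment of about 1200, or about 400 per arm.

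**The concern.** The imputed score stands for the chance that a missing infant had the event, so it cannot exceed 1. At a 10% placebo rate every delta above 10 breaks that limit. A multiplier without a bound, combined with a stop on the sign of the difference, can run past the limit when few infants are missing. The macro would give no warning, because the arm-level proportion stays far below 1.

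What is at stake is the missing-data robustness statement for the primary endpoint and, through SAP 5.7.2, for the secondary endpoint. Protocol Amendment 4 removed the worst-case analysis. The observed-case analysis in SAP 5.7.1.3 keeps all FAS subjects in the denominator, so it in effect treats missing infants as event-free. That leaves the tipping-point analysis as the only listed missing-data analysis that stresses the REGN2222 arm beyond the placebo rate. A report giving a tipping point of delta = 13 would name a scenario that cannot occur.

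**Working it through.** **Plan's own figures.** SAP 2.2 states: "The sample size calculation was based on chi-square test with continuity correction". For 10% v 4%, 90% power and 2-sided alpha 0.025, that method gives 480 evaluable per arm. 480 / 0.95 = 505.3, rounded up to 506, against 505 stated. At 2-sided 0.05 with 400 x 0.95 = 380 evaluable per arm it gives 87.4% power, which matches the stated 87%. The inputs are therefore read as the plan intends.

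**Sign reversal.** Let d be dropout, P the placebo rate, R the REGN2222 rate among infants with observed outcomes, and q = delta x P the imputed probability per missing REGN2222 infant.

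- REGN2222 proportion = (1 - d)R + dq.
- Placebo proportion = (1 - d)P + dP = P.
- The difference is zero at q = [P - (1 - d)R] / d.

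With d = 0.05, P = 0.10 and R = 0.04: q = (0.10 - 0.038) / 0.05 = 1.24, so delta = 12.4.

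In counts at 400 per arm: 20 are missing, 0.04 x 380 = 15.2 REGN2222 events are observed, and placebo has 40 events including imputed ones. Then 15.2 + 20q = 40 gives q = 1.24. The arm size cancels, so 505 per arm gives the same answer.

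| delta | q | REGN2222 | placebo |
|---|---|---|---|
| 10 | 1.0 | 8.8% | 10.0% |
| 11 | 1.1 | 9.3% | 10.0% |
| 12 | 1.2 | 9.8% | 10.0% |
| 13 | 1.3 | 10.3% | 10.0% |

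The whole-step rule stops at 13. If infants who leave are instead assumed to have had half the exposure, with events before leaving, the exact delta is 12.9 and the rule again stops at 13.

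**When it occurs.** Setting q = 1 at 10% v 4% gives d = (P - R) / (1 - R) = 0.06 / 0.96 = 6.25%. The documents give only the 5% dropout figure; the other rows are assumed.

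| dropout | q at sign reversal |
|---|---|
| 2% (assumed) | 3.04 |
| 3% (assumed) | 2.04 |
| 5% (design) | 1.24 |
| 7% (assumed) | 0.90 |

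The effect size also matters. With 5% dropout, a 10% placebo rate and an assumed 45% efficacy (R = 0.055), q = (0.10 - 0.95 x 0.055) / 0.05 = 0.955, which is possible.

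**Loss of significance.** This uses the continuity-corrected variance of SAP 5.7.1, treated as one stratum, with 400 per arm and 5% dropout. At q = 0.48 the REGN2222 proportion is 0.038 + 0.05 x 0.48 = 6.2%. The corrected proportions are (24.8 + 0.5) / 401 = 0.0631 and (40 + 0.5) / 401 = 0.1010, the standard error is 0.0193, and z = -0.038 / 0.0193 = -1.97. Two-sided 0.05 significance is therefore lost at q of about 0.48. On the SAP's whole-number grid, delta = 4 gives p = 0.028 and delta = 5 gives p = 0.056. At q = 1, p = 0.56. Unlike the sign result, this boundary depends on arm size: at 505 per arm, p is 0.032 at q = 0.5 and 0.067 at q = 0.6.

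**The case against.** The other side has four arguments.

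First, delta is a multiple of a known rate, so a reader who sees delta = 13 beside a 10% Kaplan-Meier rate can work out that no possible imputation reverses the sign. The error also cannot hide a fragile point estimate, because it arises only when that estimate survives every possible value. This stands, and it limits the severity. It does not remove the need to state the conclusion correctly.

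Second, the analysis is a sensitivity analysis whose p-values the SAP labels descriptive. A reader might infer that the primary result or its error control is compromised. The documents do not support that: the primary statistic, the testing hierarchy and the sample size do not use this rule.

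Third, the step 3 expression is garbled in the text available for review, so a bound inside it cannot be fully excluded. The note that delta = 1 equals the primary analysis and the open-ended loop support a multiplicative, uncapped reading.

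Fourth, a cap alone could make the report more reassuring than it should be. A reader might take the absence of a tipping point to mean that the efficacy conclusion survives any missing-data assumption. Only the sign does: at the design values significance is lost at about 0.48, far short of 1. This point stands and shapes the fix. Stopping at loss of significance would keep q below 1 at the 5% design dropout, though at an assumed 2% dropout and 400 per arm the boundary is 1.15, so the bound is still needed.

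**Conclusion.** The point holds at the trial's own planning values. Read as a multiplicative rule without a cap, SAP 5.7.1.3 cannot meet its stopping criterion with any possible imputed value at 10% v 4% and 5% dropout, and it would end at delta = 13.

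A reader might infer that this will happen in the actual analysis. The documents do not establish that, because the outcome depends on the observed dropout, placebo rate and effect. At 10% v 4% it needs dropout below 6.25%. The calculation assumes equal dropout in the two arms and, for the main figure, no events before early termination; the significance boundary also assumes 400 per arm and a single stratum.

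The consequence is confined to how one descriptive sensitivity analysis is reported. Severity is minor.

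**What to change.** In SAP 5.7.1.3, impute the smaller of 1 and delta x the placebo Kaplan-Meier rate, and end the loop once the imputed probability reaches 1, with 1 itself always evaluated. Report two results for each REGN2222 arm: the imputed probability at which 2-sided 0.05 significance is lost, and the one at which the sign of the difference reverses. If either is not reached at probability 1, state that no tipping point exists for that named criterion. Carry the same wording to the secondary endpoint through SAP 5.7.2, and confirm that the step 3 formula in the source SAP contains no bound already.

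The cost is one SAP sentence and a bound in the macro before database lock. No new data are needed, and the primary analysis does not change.
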